HydroEye® is a dietary supplement that contains the fatty acid, GLA from black currant seed oil, as well as the fatty acids EPA and DHA from fish oil. It also includes vitamins A, E, C, B6, and magnesium and other nutrients, many of which are involved in fatty acid metabolism. In 2013, Sheppard et al. tested HydroEye® in dry eye patients who were not contact lens wearers and found **symptom improvement, lower levels of inflammatory biomarkers and a smoother corneal surface compared with placebo..¹⁴** To date, HydroEye® has not been assessed in patients with contact lens discomfort; therefore, the purpose of this clinical trial is to determine the efficacy of a revised HydroEye® formulation (see Appendix) as a treatment for contact lens discomfort.

II. STUDY DESIGN

A. Overview and analysis plan

The proposed research study is a randomized, double-masked, controlled clinical trial to test the efficacy of HydroEye® nutraceutical in subjects with contact lens discomfort. Forty-two subjects will be recruited and randomized in a 1:1 ratio of HydroEye® to placebo. The trial will span 26 weeks, consisting of four clinical visits, two phone encounters to reinforce study drug compliance (investigator will ask about supplement usage and will ask subject contact lens survey question), and three two-week intervals of subject-entered, electronic data collection in the form of a daily diary (Figure 1). Visit 1 (V1) is the Screening Visit to ensure that patients meet all inclusion and exclusion criteria. For two weeks following V1, subjects will complete daily diary entries using Qualtrics Research Suite to assess their daily symptoms and comfortable contact lens wear time. V2 is the Baseline Visit and will occur two weeks after V1. If a subject meets all inclusion and exclusion criteria through V2, then randomization will occur, and study product will be dispensed. Six weeks after V2, staff will call and email the subject to reinforce the importance of study product compliance. V3 will occur at 3 months from V2. All clinical testing will be identical except that previous study product will be collected and new product will be dispensed. Again, phone and email reinforcement will occur 6 weeks after V3, and V4 will occur 3 months after V3. At the conclusion of the clinical trial, significant knowledge will be gained regarding the clinical utility of HydroEye® in patients with contact lens discomfort.

Testing to be performed at each clinical visit:

	Visit 1 Screening Visit	Visit 2 Baseline Visit	Visit 3 3 months	Visit 4 6 months
Informed consent	X			
Ocular and medical history, including contact lens wear history	X	X	X	X
CLDEQ-8 Questionnaire	X	X	X	X
SPEED Questionnaire	X	X	X	X
NPSI Questionnaire	X	X	X	X
Visual acuity	X	X	X	X
Slit lamp examination	X	X	X	X
Capillary tear collection	X	X	X	X
Tear break-up time		X	X	X
Corneal staining		X	X	X
Conjunctival and lid wiper staining		X	X	X

Schirmer's I Test	X	X	X	X
Meibography with Oculus Keratograph	X			
Study drug or placebo dispense	X	X	X	
Study drug collection		X	X	X
Expected Duration	45 mins	60 mins	60 mins	60 mins

B. Sample Size and Analysis

LTB₄ values will serve as a primary biological outcome for judging if HydroEye® is able to improve ocular surface health. Work from Masoudi et al. suggests that LTB₄ is significantly different between symptomatic (0.32 ± 0.06 ng/mL) and asymptomatic (0.17 ± 0.04 ng/mL) contact lens wearers. A 0.06 ng/mL difference (equivalent to one standard deviation) in LTB₄ concentration will be considered a meaningful improvement in LTB₄ concentration. Thus, 16 subjects per group will be needed to determine if there is no difference in LTB₄ concentration between groups at the final outcome visit (power = 80%; alpha = 0.05). After adjusting for 10% dropout, a total sample size of 36 subjects will be needed to determine if there is a statistical difference between subject groups.

CLDEQ-4 scores (Rasch validated version; max score of 18) will serve as the primary outcome for judging if HydroEye® is able significantly improve contact lens comfort.²⁷ Data from Pucker et al. suggests that the average contact lens wearer has a mean CLDEQ-4 score of 7.6 ± 3.8 .²⁷ A 4-point difference in CLDEQ-4 scores will be considered a meaningful improvement in CL comfort. Therefore, 19 subjects per group will be needed to determine if there is no difference in contact lens comfort between the two groups at the final outcome visit (power = 90%; alpha = 0.05). After adjusting for 10% dropout and subject withdrawals, a total sample size of 42 subjects will be needed to determine if there is a statistical difference in contact lens comfort scores between subject groups. Since the sample size based upon CLDEQ-4 is larger, 42 subjects will be recruited.

An additional 10 subjects are being requested to account screen fails, and 8 more subjects are being requested for assay protocol development. Therefore, this study is requesting a maximum of 60 subjects. If additional subjects are not needed to account for screen fails, recruitment will be stopped accordingly.

Baseline data of the active and placebo groups will be analyzed at study completion. Primary and all secondary outcomes will be compared to baseline and between groups. SPSS will be used for all analysis.

C. Objectives

CO-PRIMARY OBJECTIVE

To assess changes in comfortable contact lens wear time and subjective symptom severity (CLDEQ-4) in response to HydroEye® supplementation in those who experience contact lens discomfort

SECONDARY OBJECTIVE

To assess changes in LTB₄ levels in response to HydroEye® supplementation in those who experience contact lens discomfort

D. Endpoints

CO-PRIMARY ENDPOINTS

Mean change in the difference between overall wear time and comfortable wear time at 6 months

Mean change in CLDEQ-4 scores at 6 months

SECONDARY ENDPOINTS

Mean change in LTB₄ levels at 6 months

Mean change in SPEED scores at 6 months

Mean change in NPSI scores at 6 months

Mean change in TBUT at 6 months

Mean change in Schirmer I at 6 months

Mean change in corneal staining at 6 months

Mean change in conjunctival staining at 6 months

Mean change in lid wiper epitheliopathy at 6 months

Mean change in tear cytokine levels (RayBiotech Human Inflammation Array Q3) at 6 months

E. Inclusion Criteria

[figure not shown]
1. Age \geq 18 years
2. Provide informed consent and authorization to disclose protected health information
3. Willing to follow study protocol
4. Habitual, contact lens-corrected visual acuity of at least 20/30 in each eye
5. Wear soft contact lenses as daily wear for at least 6 hours per day and at least 5 days per week for the past 30 days
6. Have at least a 2-hour difference between overall wear time and comfortable wear time of contact lenses
7. Have symptoms consistent with Contact Lens Dry Eye based on CLDEQ-8 (score \geq 12)
8. Increased severity of dry eye symptoms with contact lens wear by at least 25% as determined by patient self-report

9. Clinical assessment that contact lens material, fit, prescription, and care system are not reasons for contact lens discomfort
10. Demonstrate at least 80% compliance in completion of daily electronic diary (submitted through Qualtrics Research Suite) between V1 and V2
11. Willing to discontinue use of any current dry eye treatment (including use of commercial hygiene masks, and except for artificial tears) for 4 weeks before randomization and during the course of the 6-month study.

F. Exclusion Criteria

1. Meibomian gland dropout $\geq 75\%$ in either eyelid
2. Any changes to the contact lens material, fit, prescription, or care system in the 30 days preceding enrollment or anticipates needing to make changes during the course of the study
3. Any systemic disease known to be associated with dry eye
4. Any significant ocular surface abnormality that could be associated with ocular surface discomfort, such as ectropion, entropion, trichiasis, infection, severe allergic conjunctivitis, severe eyelid inflammation, etc.
5. Any overnight wear of contact lenses
6. Any previous corneal surgery, including all types of corneorefractive surgery
7. Have temporary and/or permanent punctal plugs inserted
8. Use of supplemental fish oil, or seed oils from borage, evening primrose, sea buckthorn, flaxseed, or black currant within the last 60 days
9. Routine, usual dietary intake of more than 8 oz. of cold-water fatty fish (tuna, salmon, mackerel, sea bass, sardines or herring) per week).
10. Use of anticoagulant therapy or regular, daily use of aspirin, NSAIDs, or steroid medications within the past 30 days, or a history of easy bruising
11. Allergy or intolerance to fish or any ingredients contained in the active or placebo formulas [See appendix or ingredient list]
12. Participation in a clinical trial in the past 30 days
13. Current pregnancy or breast feeding as indicated by self-report

III. TIMELINE AND REPORTING

IV. BUDGET

The following budget outlines the estimated costs associated with the proposed clinical trial.

Item	Unit Cost	Total
Clinical Assessment		
Consumables (fluorescein, lissamine green, alcohol pads, charts, Schirmer strips, etc.)	-----	\$550.00
Salaries		
Clinician (3.75 h/subject * 55 subjects = 112.5 clinician hours)	\$150.00/hour	\$30,937.5
Study coordinator (0.5 hours/visit * 120 visits = 60 coordinator hours)	\$50.00/hour	\$3,000.00
Subject Compensation		
Subject Visit (\$20 for V1; \$40 for each V2-V4)	\$140.00/subject	\$4,200.00
Laboratory Assessment		
RayBiotech Human Dry Eye Disease Array Q1 (32-50 sample kit, Qty 3)	\$4,694.00	\$14,082
Enzolife Sciences LTB4 ELISA Kit (50 sample kit, Qty 3)	\$559	\$3,501
Other		
Protocol development and IRB review	\$2,500.00	\$2,500.00

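### No rule says whether one or both co-primaries must be met; the wear-time co-primary is unsized, so the stated 90% is power for CLDEQ-4 alone and not for trial success

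*Combined protocol and SAP*

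**What the plan says.** **What is primary.** II.B (Sample Size and Analysis) says that LTB4 "will serve as a primary biological outcome for judging if" the product improves ocular surface health, and it names CLDEQ-4 as the primary outcome for comfort. II.C and II.D instead list two co-primaries, wear time and CLDEQ-4. LTB4 becomes the secondary objective and heads the secondary endpoints: "Mean change in LTB₄ levels at 6 months".

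**What is sized.** II.B sizes LTB4 (16 per group, 36 in total) and CLDEQ-4 (19 per group, 42 in total). The CLDEQ-4 calculation concerns "contact lens comfort between the two groups at the final outcome visit (power = 90%; alpha = 0.05". The choice of N is then: "Since the sample size based upon CLDEQ-4 is larger, 42 subjects will be recruited". Wear time does not appear in II.B.

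**Which wear-time variable.** The II.C objective reads "To assess changes in comfortable contact lens wear time and subjective symptom severity (CLDEQ-4". The II.D endpoint is "Mean change in the difference between overall wear time and comfortable wear time at 6 months". Inclusion criterion 6 uses the same gap as II.D: "Have at least a 2-hour difference between overall wear time and comfortable wear time of contact lenses". The diary description in II.A names daily symptoms and comfortable wear time, but not overall wear time. The visit table lists contact lens wear history at all four visits.

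**How the outcomes are judged.** The analysis text is one sentence plus the choice of software: "Primary and all secondary outcomes will be compared to baseline and between groups". It gives no success rule, alpha allocation or multiplicity method.

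**The concern.** With two co-primaries and no decision rule, the efficacy claim can be settled after the data are seen. The two possible rules have different consequences. If both endpoints must succeed, alpha is protected, but the trial's power is the joint power, which was never calculated. If either is enough at 0.05, type I error rises to nearly double.

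The wear-time definition adds a second choice. Comfortable wear time can rise with the gap unchanged, if overall wear time rises too. The gap can shrink simply because a subject wears lenses for fewer hours. The two variables could therefore give different answers from the same trial.

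A third choice is the form of the comparison. II.B sizes a between-group difference at the final visit, II.D defines mean change, and the analysis sentence adds comparison with baseline. No SD of change is given.

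**Working it through.** **Inputs from II.B.** CLDEQ-4: difference 4, SD 3.8, power 90%, alpha 0.05, 19 per group. LTB4: difference 0.06 ng/mL, equal to 1 SD, power 80%, alpha 0.05, 16 per group. Sidedness is not stated; two-sided is inferred because the normal approximation gives 19 and 16 two-sided, but 16 and 13 one-sided.

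**Assumed, because the documents give no values.** Wear-time effects in SD units, the correlation between the co-primaries, and the baseline-to-final correlation of CLDEQ-4.

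**1. The plan's own sizes reproduce.** n per group = 2(z₀.₉₇₅ + z_power)² / d².
- CLDEQ-4: d = 4/3.8 = 1.053; 2(1.960 + 1.282)² / 1.053² = 18.97, so 19.
- LTB4: d = 1; 2(1.960 + 0.842)² = 15.70, so 16.
- Total for CLDEQ-4: 38 × 1.1 = 41.8, so 42.

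**2. CLDEQ-4 power at 19 per group.**
- Normal approximation: Φ(1.053 × √(19/2) − 1.960) = Φ(3.244 − 1.960) = 90.05%.
- Two-sample t-test (noncentral t, 36 df): 88.4%.

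**3. If both are required.** Joint power cannot exceed the lower of the two single powers, so CLDEQ-4's own power is a ceiling. Joint power comes from a bivariate normal with the two single t-test powers as margins, 19 per group:

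| Assumed wear-time effect | Wear-time power | Joint, correlation 0 | Joint, correlation 0.5 |
|---|---|---|---|
| 0.5 SD | 32% | 29% | 31% |
| 0.8 SD | 67% | 59% | 63% |
| 1.0 SD | 85% | 75% | 78% |
| 1.05 SD | 88% | 78% | 81% |

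At correlation 0 this is a product: 0.884 × 0.884 = 0.782. Wear time alone reaches 80% power at an effect of 0.93 SD and 90% at 1.08 SD.

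**4. If either sufficed, each at two-sided 0.05.**
- Independent: 1 − 0.95² = 9.75%. Correlation 0.5: 9.1%.
- Benefit direction only: 1 − 0.975² = 4.9% (4.5% at correlation 0.5), against 2.5% for one test.
- Under Holm, CLDEQ-4 power at the 0.025 step is 81% by t-test and 84% by normal approximation.

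**5. Final value, unadjusted change or baseline-adjusted.** Take SD 3.8 at both visits and baseline-to-final correlation ρ.
- Change: SD = 3.8√(2(1 − ρ)). At ρ = 0.3 this is 4.50 and power is 76% (t) to 78% (normal). At ρ = 0.5 the SD is 3.80 and power is 88% to 90%, as planned. At ρ = 0.7 the SD is 2.94 and power is 98% to 99%.
- Baseline-adjusted: SD = 3.8√(1 − ρ²). At ρ = 0.3 this is 3.62, d = 4/3.62 = 1.10, and power is 91% (t) to 93% (normal).

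**The case against.** **Co-primary conventionally means both.** This is the fairest reading: the label, and the conjunction in the II.C objective, point that way. A reader might infer from step 4 that the trial runs at nearly 10% type I error. The documents do not support that, because they nowhere say that either endpoint suffices. The objection does not remove the point, since under the both-required reading the 90% is not the power for success.

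**The deciding comparison can be read from II.B.** This largely stands. II.B frames the CLDEQ-4 and LTB4 questions as differences between groups, in a randomised placebo-controlled trial. What remains open is narrower: final value or change, adjusted or not, and what role the comparison with baseline plays.

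**Change instead of final value need not lose power.** Correct. The result straddles 90% and equals the planned power at ρ = 0.5. The finding is an unstated assumption, not a shown loss.

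**The wear-time effects are assumptions.** They are. A reader might infer that wear time is under-powered, but without a target difference or SD the documents cannot show that. They show only that it was not sized.

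**The LTB4 label and the wording of II.C are editorial.** Mostly accepted. N rests on CLDEQ-4, so the label does not change it. II.D is the more specific text and agrees with inclusion criterion 6, so it reasonably governs. Both still need correcting, because the two wear-time variables can diverge.

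**Conclusion.** The point holds. The main defects are the missing one-or-both rule and a power statement that covers one co-primary only. The LTB4 label and the mismatch between II.C and II.D are lesser corrections.

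Under the reading the text favours, alpha is held at 0.05 and the stated 90% (88.4% by t-test) is a ceiling on power for success in the comparison that was sized. With assumed correlation 0 to 0.5, joint power by t-test is 78% to 81% if wear time has a 1.05 SD effect and 59% to 63% at 0.8 SD. The 9.1% to 9.75% error applies only if either endpoint were allowed to suffice unadjusted.

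The sample-size arithmetic is not at fault: 19 and 16 per group reproduce. The existence of the gaps is certain from the text; the joint-power figures depend on the assumed effects and correlations.

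**What to change.** Before unmasking, with N kept at 42:

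1. **Decision rule.** State that success requires both co-primaries to favour HydroEye over placebo, each at two-sided 0.05 with no alpha split, in a between-arm comparison at 6 months adjusted for the baseline value (ANCOVA). Within-arm comparisons with baseline are descriptive only. If the sponsor means either to suffice, use Holm across the two.
2. **Power statement.** State that 42 was sized on CLDEQ-4 alone, from a final-visit difference, and that 90% is not the power for trial success. Tabulate wear-time and joint power at 19 per group over a stated range of effects and correlations.
3. **Wear-time variable.** Use the II.D gap in II.C as well, and name the data source of each component. As the diary text names only comfortable wear time, either confirm or add an overall wear-time item in the diary, or name the wear history taken at each visit as the source.
4. **LTB4.** Relabel it as secondary in II.B.

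**Cost.** No added subjects: one rule, one power table, one endpoint definition with its sources, one relabel, and possibly one diary item. The downside is that, on the basis used for sizing, the stated power for trial success falls below 90%. If the sponsor wanted 90% joint power on that basis, the t-test would need 24 to 25 completers per group for an assumed 1.05 SD wear-time effect, or 35 for 0.8 SD, against 19 now.

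### CLDEQ-4 is powered on final-visit scores but its co-primary endpoint is change at 6 months, and no deciding analysis is named; a between-arm ANCOVA on baseline would align the two

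*Combined protocol and SAP*

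**What the plan says.** Section II.B (Sample Size and Analysis) takes its SD from a statement that "the average contact lens wearer has a mean CLDEQ-4 score of 7.6 ± 3.8". It treats 4 points as meaningful and asks for 19 subjects per group to assess a "difference in contact lens comfort between the two groups at the final outcome visit (power = 90%; alpha = 0.05"). After 10% dropout the total is 42, described as enough to detect "a statistical difference in contact lens comfort scores between subject groups".

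Section II.D (Endpoints) defines the CLDEQ-4 co-primary as "Mean change in CLDEQ-4 scores at 6 months". The other co-primary is "Mean change in the difference between overall wear time and comfortable wear time at 6 months".

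The only analysis sentence, at the end of II.B, is "Primary and all secondary outcomes will be compared to baseline and between groups", followed by the name of the software. The plan gives no test, model or covariate, no SD of change and no baseline-to-final correlation.

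Section II.A places randomization at V2, once entry criteria are met, so the V2 score is a pre-randomization baseline.

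**The concern.** The contrast that was powered and the endpoint that was defined are not the same quantity. A final-score comparison has variance governed by the SD of one score. A change-score comparison has variance governed by the SD of the difference between two scores, which depends on r. The stated 90% therefore does not carry over to a change-score test without a further assumption that the plan does not make.

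A final-score test, a change-score test and a baseline-adjusted test all fit the text. With 42 subjects they can give different p-values and intervals, and nothing in the plan fixes the choice in advance. Comparison with baseline also stands unranked beside the between-group comparison. A within-arm change mixes any treatment effect with placebo response. Because subjects enter on high symptoms (CLDEQ-8 of at least 12), it may also include regression to the mean.

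**Working it through.** **Inputs from II.B:** difference 4 points; SD 3.8; alpha 0.05, taken as two-sided because that reproduces the stated n; 19 per group; 10% dropout; total 42.

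**Assumptions:** SD 3.8 at both visits; r of 0.3, 0.5 and 0.7, since the documents give no value; completers per arm 21 × 0.9 = 18.9, so N = 37.8.

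**1. The plan's own figure.** Normal approximation: n = 2 × ((1.96 + 1.2816) × 3.8 / 4)² = 18.97, so 19 per group, which matches. Then 38 × 1.10 = 41.8, so 42, which also matches. The exact t calculation gives 88.4% at 19 per group and 90.0% at 20. The one-sided version gives 16 and does not match. The 19 is therefore a two-sided comparison of final scores.

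**2. Formulas at 18.9 per arm (noncentral t).**
- Noncentrality = 4 / (SD × √(2/18.9)).
- Final score: SD = 3.8, df = N − 2.
- Unadjusted change: SD = 3.8 × √(2(1 − r)), df = N − 2.
- ANCOVA: SD = 3.8 × √(1 − r²), df = N − 3, with the variance multiplied by 1 + 1/(N − 4) = 1 + 1/33.8 = 1.030 to allow for chance baseline imbalance.

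**3. Results.**

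| Analysis | r = 0.3 | r = 0.5 | r = 0.7 |
|---|---|---|---|
| Final score, power | 88.3% | 88.3% | 88.3% |
| Change, SD | 4.50 | 3.80 | 2.94 |
| Change, power | 75.8% | 88.3% | 98.2% |
| ANCOVA with imbalance, power | 90.1% | 94.7% | 99.1% |
| Final score, 95% CI half-width | 2.51 | 2.51 | 2.51 |
| Change, 95% CI half-width | 2.97 | 2.51 | 1.94 |
| ANCOVA with imbalance, 95% CI half-width | 2.43 | 2.21 | 1.82 |

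**4. Thresholds.** Two need to be kept apart. The change-score test equals the final-score test at r = 0.5, where the SD of change is 3.80. It reaches a literal 90% only at r = 0.53, where the SD of change is 3.69. By that stricter standard the final-score test also falls slightly short, at 88.3%.

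**5. ANCOVA against the final-score test.** From unrounded figures, the gain with the imbalance allowance is 1.9 points at r = 0.3 and 6.5 at r = 0.5. It breaks even at r = 0.17. At r = 0 it loses about one point (87.3% against 88.3%).

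**6. Sensitivity to entry selection.** Selecting symptomatic subjects can narrow the spread of scores. As an illustration only, simulated normal scores (mean 7.6, SD 3.8) were cut at 7.6 on CLDEQ-4 at both V1 and V2. This is not the protocol's CLDEQ-8 criterion. At r = 0.3 the final-score test and ANCOVA with imbalance then both have 91.0%, and change has 85.1%. At r = 0.5 the figures are 94.6% for final score, 95.8% for ANCOVA with imbalance and 92.9% for change. The gain over a final-score test may therefore be close to nil at low r.

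**The case against.** The strongest reply is that nothing here is invalid. In a 1:1 randomized trial, final-score and change-score comparisons both estimate the between-arm difference without bias. The stated n reproduces, and at r of 0.5 or more a change-score test does at least as well as the powered contrast. II.B also speaks twice of a difference between groups, so the between-arm test is the natural reading of the efficacy analysis. On this view ANCOVA is a preference.

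Much of this stands. A reader might infer that the trial is underpowered for its co-primary. The documents do not support that: the 75.8% figure rests wholly on an assumed r of 0.3, and r is not given. A reader might also infer that a within-arm test is the planned test of efficacy. The documents do not say so; they only leave it unranked. Final-score and change-score tests would each be defensible if named in advance.

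What the reply does not answer is that no test is named. The between-group wording in II.B does not choose among final-score, change-score and adjusted analyses. ANCOVA is more than a matter of taste here. It gives the same treatment effect whether the outcome is written as final score or change, so it reconciles II.B with II.D without altering the endpoint or the sample size. Across r from 0.3 to 0.7 its power moves by 9 points (90.1 to 99.1%), against about 22 for the change-score test (75.8 to 98.2%).

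**Conclusion.** The point holds as a mismatch and an under-specification. It is not an arithmetic error or a demonstrated loss of power. The CLDEQ-4 power applies to final-visit scores, the endpoint is change, and the deciding analysis is unnamed. Depending on the unstated r, an unadjusted change-score test could have clearly less or clearly more power than the contrast that was sized. ANCOVA equals or exceeds the final-score test once r reaches about 0.17, and costs about one point at worst for r of 0 or more.

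These figures cover CLDEQ-4 only and rest on SD 3.8 at both visits, a 4-point difference, 18.9 completers per arm and assumed values of r. Confidence is high in the omission and in the direction of the fix. The size of the gain is uncertain, and it may be negligible at low r if entry selection narrows the spread. This should be fixed before unblinding.

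**What to change.** - **CLDEQ-4:** name as the deciding analysis a between-arm ANCOVA of the 6-month score on arm, with the pre-randomization V2 score as covariate. Report the adjusted difference with a 95% CI. State how CLDEQ-4 is obtained, since the visit schedule lists CLDEQ-8.
- **Within-arm comparisons with baseline:** label them descriptive.
- **Power:** restate the CLDEQ-4 power for this analysis over an assumed range of r, for example 0.3 to 0.7.
- **Wear time:** use the same model with its own pre-randomization baseline, and name the data source. Entry criterion 6 uses the gap ("Have at least a 2-hour difference between overall wear time and comfortable wear time of contact lenses"), but II.A describes the diary as serving "to assess their daily symptoms and comfortable contact lens wear time" and does not mention overall wear time. State no power for this endpoint unless an SD and effect size are supplied.
- **Baseline timing:** II.A places randomization and dispensing at V2, while the visit schedule also marks dispensing at V1. The two must be reconciled so that the baseline is clearly pre-randomization.

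The cost is analysis-plan wording, one degree of freedom, and about one point of power if baseline proves uninformative. The covariate is the baseline value that each change endpoint already needs. How the two co-primaries combine is a separate matter that this change does not settle.

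### The wear-time co-primary gives its best value to a subject who has stopped wearing lenses, and the plan has no scoring rule for such subjects on either co-primary.

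*Combined protocol and SAP*

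**What the plan says.** Section II.D lists two co-primary endpoints: "Mean change in the difference between overall wear time and comfortable wear time at 6 months" and "Mean change in CLDEQ-4 scores at 6 months". The objective behind them in II.C is "To assess changes in comfortable contact lens wear time and subjective symptom severity (CLDEQ-4) in response to HydroEye® supplementation". It names comfortable wear time itself, not its distance from overall wear time.

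Lens wear is a condition of entry only. Item 5 of II.E reads "Wear soft contact lenses as daily wear for at least 6 hours per day and at least 5 days per week for the past 30", counted in days, and item 6 reads "Have at least a 2-hour difference between overall wear time and comfortable wear time of contact lenses". Nothing requires lens wear after randomisation.

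On data collection, II.A says that after the screening visit "subjects will complete daily diary entries using Qualtrics Research Suite to assess their daily symptoms and comfortable contact lens wear time"; overall wear time is not mentioned there. The visit table schedules the CLDEQ-8 at every visit, and II.B names the CLDEQ-4 as the measure of lens comfort. Neither its items nor its recall period is given.

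The analysis text is one sentence: "Primary and all secondary outcomes will be compared to baseline and between groups". The plan gives no analysis set, no missing-data method and no rule for events such as stopping lens wear. Dropout appears only as a 10% increase in sample size.

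**The concern.** Both co-primaries presuppose that lenses are being worn. The trial enrols people selected for lens discomfort and follows them for six months, so some may stop wearing lenses, skip days or take lenses out early. Each of these can reduce the gap without adding a comfortable hour. A subject may take all the product, attend the final visit and still be scored this way, so allowing for dropout does not cover the case.

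If the product works, stopping because of discomfort should be more frequent on placebo. Scoring those subjects as fully improved, or losing them, would flatter placebo. Without a rule, someone must choose between best score and exclusion after the data are in, on a co-primary of a 42-subject trial.

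**Working it through.** **1. The plan's own figure.** Inputs from II.B: difference 4, SD 3.8, two-sided alpha 0.05 (sidedness assumed), power 90%. n = 2 × [3.8 × (1.960 + 1.282) / 4]² = 18.97, so 19 per group as stated. 38 × 1.1 = 41.8, so 42. The sample-size arithmetic is not at issue. With 42 randomised 1:1 there are 21 per arm, and the t-test power with all observed is 91%.

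**2. The gap for a stopper.** Gap = overall − comfortable. Comfortable time cannot exceed overall time, so the minimum and best value is 0. A non-wearer has 0 − 0 = 0. Change = 0 − baseline gap, and item 6 makes the baseline gap at least 2 h, so the recorded improvement is at least 2 h and the largest open to that subject. On comfortable wear time the same subject has 0 h, the worst value.

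**3. Partial non-wear.** A subject with a 2 h gap who removes lenses 1 h earlier, with comfortable hours unchanged, has a gap of 1 h: a 1 h improvement with no gain in comfort.

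**4. Illustrative effect on the gap.** Assumptions, none from the documents: 21 per arm; continuing wearers improve 2 h on active and 1 h on placebo; 1 active and 4 placebo subjects stop and are scored 0; mean baseline gap G.
- Active mean improvement = (20 × 2 + G) / 21
- Placebo mean improvement = (17 × 1 + 4G) / 21
- Apparent benefit = (23 − 3G) / 21

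| G (h) | Apparent benefit (1.0 h among wearers) |
|---|---|
| 2 | 0.81 |
| 3 | 0.67 |
| 4 | 0.52 |
| 6 | 0.24 |

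If wearers improve 1 h in both arms, the result is (3 − 3G) / 21, which favours placebo by 0.14 h (G = 2) to 0.71 h (G = 6). With k stoppers in each arm the benefit is (21 − k) / 21, that is 0.95 h for k = 1 and 0.90 h for k = 2: slight dilution only.

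**5. Illustrative effect on CLDEQ-4.** Simulation of 40,000 trials: normal scores, means 3.6 (active) and 7.6 (placebo), SD 3.8, 21 per arm, two-sided 5% tests. Stoppers are assumed to be the highest scorers in their arm. Three treatments of stoppers are compared: dropped (t-test), set to 18 (t-test), or given the worst rank (rank-sum test).

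| Stoppers (active, placebo) | Mean difference if dropped | Power, dropped | Power, set to 18 | Power, worst rank |
|---|---|---|---|---|
| 0, 0 | 4.0 | 91% | 91% | 90% |
| 0, 1 | 3.6 | 87% | 92% | 90% |
| 0, 2 | 3.3 | 81% | 93% | 90% |
| 0, 3 | 3.1 | 74% | 95% | 91% |
| 1, 1 | 4.0 | 93% | 82% | 89% |
| 1, 2 | 3.7 | 89% | 85% | 89% |
| 2, 2 | 4.0 | 94% | 67% | 86% |

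With 2 stoppers per arm set to 18, the pooled SD rises from 3.8 to about 5.05, a standard error about 33% larger.

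**The case against.** Four points can be made against this.

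- **CLDEQ-4.** A reader might infer that a stopper simply has no CLDEQ-4 score. The documents do not support that. The questionnaire is scheduled for everyone at the final visit, and a recent stopper might answer from memory or score near zero. What stands is that the value is undefined.
- **Zero gap.** This is one reading. The diary form is not shown, and a day without lenses may be blank instead of 0 and 0. That objection stands too, but blank means missing, and the plan has no rule for that either.
- **Frequency and direction.** A reader might infer that the trial is certainly biased against the product. No stopping rate, mean gap or gap SD is given. Entrants are established wearers, and those expecting lens or care-system changes are excluded, so stopping may be rare. Bias toward no effect needs more stopping on placebo; more on active would reverse it.
- **Size.** A reader might remove stoppers from 19 per arm and find larger power losses. But 19 is the number left after the 10% allowance, so that counts loss twice; 21 per arm are randomised.

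None of these supplies the missing rule, and the conflict between endpoint and objective does not depend on how often stopping occurs.

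**Conclusion.** The point holds. By its own definition, the wear-time co-primary rates a non-wearer as best while the objective's quantity rates the same subject as worst. No section says how such a subject, or a day without lenses, is scored. That part follows from the text and arithmetic.

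The CLDEQ-4 part is weaker: undefined, not necessarily lost. That stopping because of discomfort is a bad outcome is a reasonable reading of a lens-discomfort trial, but the documents do not state it. The sizes are illustrative and rest on assumed stopper counts, on stoppers being the worst CLDEQ-4 scorers and, for the gap, on assumed changes among wearers. The loss ranges from none to moderate, according to how unequal stopping is between arms. This should be settled before unmasking; it does not invalidate the design.

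**What to change.** Add to II.D:

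- A subject who has stopped lens wear because of discomfort by V4, or a diary day without lenses for that reason, is never scored as a zero gap. Define stopping in terms of the final diary interval.
- Such subjects stay in both co-primary comparisons, ranked below all continuing wearers, with a rank-based test. Do not use a mean with 18, or baseline wear time, filled in: two stoppers per arm set to 18 cut power to about 67%, against about 86% by worst rank.
- Diary days off lenses for other reasons are left out of the mean.
- Comfortable wear hours and the number of lens stoppers are reported by arm. The hours match the objective and also show early removal, which the gap conceals.

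Add one diary item: were lenses worn today and, if not, was discomfort the reason?

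The cost is a few lines of analysis text and one diary question. With no stoppers the rank test gives up a little power (about 90% against 91%). With equal stopping it has less power than dropping the worst scorers (86% against 94% at two per arm), because it counts failures that dropping ignores. The effect is no longer a simple mean difference, so the means among continuing wearers should be shown alongside as description.
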